### 9.2.3 DUSP4 Expression

Quantitative gene expression levels for DUSP4 and several control genes (defined in Balko et al.) will be detected using real-time PCR with the ABI PRISM 7900HT Sequence Detection System (Applied Biosystems, Foster City, CA) and TaqMan MGB probes (FAM dye labeled). Primers and probes for all genes analyzed will be purchased from Applied Biosystems Assays-on-Demand Gene Expression products. Total RNA will be purified from tissue as previously described and will be used to synthesize cDNA for RT-PCR reactions. Relative quantification will be applied using a standard curve method and normalization to control gene expression.

### 9.2.4 Additional Studies

It is anticipated that future studies will include evaluation of genetic, epigenetic, immunologic, hormonal, and/or other issues related to breast cancer. In particular, we will be collecting and storing plasma samples to test future potential circulating biomarkers. We will inform participants in the informed consent document that we may use their specimens for research related to breast cancer and other cancers.

## 9.3. Site(s) Performing Correlative Studies

- IHC assay and DUSP4 expression analysis will be performed at the OSU Solid Tumor Translational Science Shared Resource.
- Whole exome and transcriptome sequencing will be performed at the Broad Institute.
- The RPPA assay will be performed by MD Anderson Cancer Center RPPA-Functional Proteomics Core Facility.
- The kinome assay will be performed in the laboratory of [name] at the University of North Carolina at Chapel Hill.

## 9.4 Potential risks and procedures for minimizing risks

### 9.4.1 Risks of blood draws

All blood draws will be performed by trained personnel that use standard sterile techniques. Infection is unlikely since stringent aseptic techniques are followed during all venipuncture procedures.

### 9.4.2 Risks of biopsy

The risks of this study relate primarily to the risk of a biopsy. In general, these procedures are associated with a small risk of pain, bleeding, infection, and damage to adjacent organs. The magnitude of this risk depends somewhat upon the site of the procedure.

Potential risks according to site are:

#### Risks of core breast biopsy:

- Likely: local discomfort and minor bleeding.
- Less likely: moderate or major bleeding, need for blood transfusion, hospitalization due to bleeding or other complications, infection, pneumothorax, damage to adjacent organs.

#### Risks of skin/chest wall punch biopsy:

- Likely: local discomfort and minor bleeding.
- Less likely: moderate or major bleeding, or infection

#### Risks of lymph node or soft tissue core needle biopsy:

- Likely: local discomfort and minor bleeding.
- Less likely: moderate or major bleeding, need for blood transfusion, hospitalization due to bleeding or other complications, infection, pneumothorax, damage to adjacent organs.
- Additional risks may be present if i.v. conscious sedation is required.

#### Risks of liver core needle biopsy:

- Likely: local discomfort and minor bleeding
- Less likely: moderate or major bleeding, need for blood transfusion, hospitalization due to bleeding or other complications, infection, bowel perforation or damage to adjacent organs
- Additional risks may be present if i.v. conscious sedation is required.

#### Lung biopsy core needle biopsy

- Likely: local discomfort and minor bleeding
- Less Likely: moderate or major bleeding, need for blood transfusion, lung collapse, hospitalization due to bleeding or other complications, infection,

damage to nearby organs, allergic reaction to the numbing medicine

In order to minimize the risk of a biopsy, only qualified personnel will perform these procedures. Prior to the procedure, the physician performing the procedure will discuss the risks with each study participant, answer any questions, and obtain separate procedure consent. For biopsies of lesions that are not superficial and clearly palpable, imaging studies such as CT, ultrasound, or MRI will be used to guide the biopsy in order to minimize the risk of damage to adjacent structures. After lymph node biopsies, patients will be observed for approximately 2 hours (range 2-4 hours) after the procedure, or per institutional standard guidelines. After liver biopsies, patients will be observed for approximately 4 hours (range 4-6 hours) after the procedure, or per institutional standard guidelines. Less than the goal quantity of tissue is acceptable for each type of biopsy, and will be left to the clinical judgment of the physician performing the procedure.

All grade 3 or 4 events attributable to any of the study procedures will be reported to the Principal Investigator within 24 hours of occurrence. Adverse events will be reported by the PI to the IRB consistent with standard procedures.

### **9.4.3 Anesthesia Risk**

#### Risks of local anesthesia

All biopsy procedures require local anesthesia using lidocaine, xylocaine, or related compounds. There is a small risk of an allergic reaction associated with these drugs.

In order to minimize the risk of local anesthesia, only qualified personnel will perform the biopsy procedure. Patients will be queried if they have had previous allergic reactions to local anesthetics.

#### Risks of intravenous conscious sedation

Certain biopsy procedures, such as lymph node or liver biopsies, may require intravenous conscious sedation (IVCS). IVCS is a minimally depressed level of consciousness that retains the patient's ability to maintain a patent airway independently and continuously and respond appropriately to physical stimulation and verbal commands.

The risks of intravenous conscious sedation include: inhibition of the gag reflex and concomitant risk of aspiration, cardiopulmonary complications (myocardial infarction, cardiac arrhythmias, hypoxemia), and allergic reactions to the sedative or analgesic medications. These risks are small but real; for example, in a prospective study of 14,149 patients undergoing IVCS during upper gastrointestinal endoscopies, the rate of immediate cardiopulmonary events was 2 in 1000. The 30-

day mortality was 1 per 2,000 cases. In this study, there was a strong association between lack of monitoring and use of high-dose benzodiazepines with adverse outcomes. There was also an association between the use of local anesthetic sprays to the oropharynx and the development of pneumonia.

In order to minimize the risk of intravenous conscious sedation, only qualified personnel will be responsible for conscious sedation as per institutional protocols. A minimum of two individuals will be involved in the care of patients undergoing conscious sedation—the physician performing the biopsy procedure, and the individual (M.D. or R.N.) who monitors the patients and his/her response to both the sedation and the procedure, and who is capable of assisting with any supportive or resuscitative measures. The room where the procedure utilizing IVCS takes place will have adequate equipment to provide supplemental oxygen, monitor vital signs, and maintain an airway should this be necessary. An emergency cart will also be immediately accessible to the room where the procedure is to take place, and emergency support services will be available on page. Patients will be screened and evaluated for their fitness to undergo conscious sedation by a trained physician. Following the procedure, patients will be observed closely in the recovery room according to standard institutional guidelines.

#### **9.4.4 Risk of imaging studies**

Some biopsy procedures require imaging studies, either to plan or guide the procedure. Imaging studies that may be used in obtaining tissue samples include CT scans and ultrasound. CT scans will expose study participants to controlled amounts of radiation. The total dose of radiation from these tests is not anticipated to cause any adverse effects. There is also a risk of an allergic reaction to the intravenous contrast dye used during CT imaging, as well as a risk of experiencing feelings of anxiety or claustrophobia while undergoing a CT scan. There are no anticipated risks with the use of ultrasound.

In order to minimize these risks, patients will be queried, as per standard institutional practice, regarding their history of reactions to intravenous contrast dye. If a patient has had such a reaction, she/he will be premedicated, or dye will not be used, as per standard institutional practice. If a patient has previously experienced anxiety or claustrophobia while undergoing a CT scan, anxiolytics may be considered as indicated.

## 10. STUDY CALENDAR

Baseline evaluations are to be conducted within 2 weeks prior to start of protocol therapy. Scans and x-rays must be done  $\leq 4$  weeks prior to the start of therapy. In the event that the patient's condition is deteriorating, laboratory evaluations should be repeated within 48 hours prior to initiation of the next cycle of therapy. Appropriate delays in study treatment or procedures are allowed to adjust for holidays or weekends.

### Study Calendar

Study Assessment s 	Screen	Part 1 Trametinib monotherapy	Part 2 Trametinib in combination with GSK2141795	Final Study Visit 	Post Treatment Follow Up 
Informed Consent	X				
Baseline Demographics	X				
Medical History / Interim History	X	Day 1 ( $\pm 3$ days) of each cycle	Day 1 ( $\pm 3$ days) of each cycle	X	
Concomitant Medications	X	Continuous			
Physical Exam	X	Day 1 ( $\pm 3$ days) of each cycle	Day 1 ( $\pm 3$ days) of each cycle	X	
ECOG Performance Status	X	Day 1 ( $\pm 3$ days) of each cycle	Day 1 ( $\pm 3$ days) of each cycle	X	
Vital Signs (BP, HR, Temperature, weight)	X	Day 1 ( $\pm 3$ days) of each cycle	Day 1 ( $\pm 3$ days) of each cycle	X	
Hematology, Clinical Chemistry 	X	Day 1 ( $\pm 3$ days) of each cycle	Day 1 ( $\pm 3$ days) of each cycle	X	
Pregnancy Test 	X				
Hemoglobin A1C, TSH, fasting glucose	X	Repeated every 3 cycles $\pm 7$ days or as Clinically Indicated			
Fingerstick blood glucose			At home daily monitoring for weeks 1 -4, then as clinically indicated	As Clinically Indicated	
12-Lead ECG	X		Prior to dosing on Week 1 day 1 and day 15, and then every 4 weeks (Week 5, Week 9, etc.) $\pm 7$ days or as clinically indicated		

Study Assessments 	Screen	Part 1 Trametinib monotherapy	Part 2 Trametinib in combination with GSK2141795	Final Study Visit 	Post Treatment Follow Up 
LVEF (ECHO)	X	Repeated every 3 cycles $\pm$ 7 days during Part 1 or as Clinically Indicated	Week 5, Day 1 of Part 2 and then at the start of every 12 weeks $\pm$ 7 days or as clinically indicated	As Clinically Indicated	
Ophthalmic Exam 	X	As Clinically Indicated			
Blood sample 		Day 1 ( $\pm$ 3 days) of cycle 1			
Plasma 	X	Day 1 cycle 2 and at progression	Day 1 of cycle 2 (prior to dosing)	X	
Research Biopsy(s) 	Mandatory research biopsies will be attempted on all patients prior to the initiation of study treatment on Part 1	Mandatory research biopsies will be attempted on all patients at time of progression on Part 1	Optional research biopsies will be attempted on patients at time of progression on Part 2		
Study Agents		Trametinib will be administered daily in Part 1. Trametinib will be administered in combination with GSK2141795 in Part 2. Please see Section 6 for Dose Modifications.			
Tumor measurements 	X	Staging will occur after every 2 cycles $\pm$ 7 days or as Clinically Indicated			
Adverse Events		Continuous			
Follow Up Data 					X

1. Assessments scheduled on days of dosing should be done prior to administration of study drug(s), unless otherwise specified.
2. Tumor measurements within 4 weeks of first dose. Documentation (radiologic) must be provided for patients removed from study for progressive disease. If subject was withdrawn due to progression of disease (PD), disease assessments do not need to be repeated at the Final Study Visit. CT chest/abdomen/pelvis preferred. Bone scan, MRI, PET scan may be used at the discretion of the treating physician.
3. Final Study Visit should occur 21 days ( $\pm$ 7 days) after last dose of study drug. Follow up will continue for 52 weeks after removal from study or until death, whichever occurs first. Follow up will be every 3 months to confirm patient's living status and whether the patient has progressed (if patient did not progress on protocol therapy) gathered from clinic notes or telephone calls (no patient visit required).
4. Should include alkaline phosphatase, total bilirubin, creatinine, glucose, potassium, SGOT, SGPT, sodium.
5. Perform only in women of child-bearing potential.
6. Ophthalmic exam will include indirect and direct fundoscopy, visual acuity, visual field examination, tonometry and color fundus photos. Additional ophthalmic exams will be performed if symptomatically warranted.

Study Assessment s 	Screen	Part 1 Trametinib monotherapy	Part 2 Trametinib in combination with GSK2141795	Final Study Visit 	Post Treatment Follow Up 
---------------------------------	--------	-------------------------------------	---	-----------------------------------	--

7. Whole blood (6 mL) should be collected in an EDTA tube and stored at -70°C or below until shipping.
8. Plasma should be purified from 10 mL of blood collected in an EDTA tube. Aliquots should be stored at -70°C or below until shipping.
9. Research biopsies may include breast core biopsy, skin or chest wall biopsy, lymph node biopsy, liver biopsy, or lung biopsy.

## 11. MEASUREMENT OF EFFECT

### 11.1. Antitumor Effect – Solid Tumors

For the purposes of this study, patients should be re-evaluated for response every 8 weeks. In addition to a baseline scan, confirmatory scans should also be obtained every 8 weeks following initial documentation of objective response.

Response and progression will be evaluated in this study using the new international criteria proposed by the revised Response Evaluation Criteria in Solid Tumors (RECIST) guideline (version 1.1). Changes in the largest diameter (unidimensional measurement) of the tumor lesions and the shortest diameter in the case of malignant lymph nodes are used in the RECIST criteria.

#### 11.1.1 Definitions

Evaluable for toxicity. All patients will be evaluable for toxicity from the time of their first treatment with trametinib and GSK 214179.

Evaluable for objective response. Only those patients who have measurable disease present at baseline, have received at least one cycle of therapy, and have had their disease re-evaluated will be considered evaluable for response. These patients will have their response classified according to the definitions stated below. (Note: Patients who exhibit objective disease progression prior to the end of cycle 1 will also be considered evaluable)

Evaluable Non-Target Disease Response. Patients who have lesions present at baseline that are evaluable but do not meet the definitions of measurable disease, have received at least one cycle of therapy, and have had their disease re-evaluated will be considered evaluable for non-target disease. The response assessment is based on the presence, absence, or unequivocal progression of the lesions.

#### 11.1.2 Disease Parameters

Measurable disease. Measurable lesions are defined as those that can be accurately measured in at least one dimension (longest diameter to be recorded) as  $\geq 20$  mm by chest x-ray or as  $\geq 10$  mm with CT scan, MRI, or calipers by clinical exam. All tumor

measurements must be recorded in millimeters (or decimal fractions of centimeters).

Note: Tumor lesions that are situated in a previously irradiated area may be considered measurable.

Malignant lymph nodes. To be considered pathologically enlarged and measurable, a lymph node must be  $\geq 15$  mm in short axis when assessed by CT scan (CT scan slice thickness recommended to be no greater than 5 mm). At baseline and in follow-up, only the short axis will be measured and followed.

Non-measurable disease. All other lesions (or sites of disease), including small lesions (longest diameter  $< 10$  mm or pathological lymph nodes with  $\geq 10$  to  $< 15$  mm short axis), are considered non-measurable disease. Bone lesions, leptomeningeal disease, ascites, pleural/pericardial effusions, lymphangitis cutis/pulmonitis, inflammatory breast disease, and abdominal masses (not followed by CT or MRI), are considered as non-measurable.

Note: Cystic lesions that meet the criteria for radiographically defined simple cysts should not be considered as malignant lesions (neither measurable nor non-measurable) since they are, by definition, simple cysts.

‘Cystic lesions’ thought to represent cystic metastases can be considered as measurable lesions, if they meet the definition of measurability described above. However, if non-cystic lesions are present in the same patient, these are preferred for selection as target lesions.

Target lesions. All measurable lesions up to a maximum of 2 lesions per organ and 5 lesions in total, representative of all involved organs, should be identified as **target lesions** and recorded and measured at baseline. Target lesions should be selected on the basis of their size (lesions with the longest diameter), be representative of all involved organs, but in addition should be those that lend themselves to reproducible repeated measurements. It may be the case that, on occasion, the largest lesion does not lend itself to reproducible measurement in which circumstance the next largest lesion which can be measured reproducibly should be selected. A sum of the diameters (longest for non-nodal lesions, short axis for nodal lesions) for all target lesions will be calculated and reported as the baseline sum diameters. If lymph nodes are to be included in the sum, then only the short axis is added into the sum. The baseline sum diameters will be used as reference to further characterize any objective tumor regression in the measurable dimension of the disease.

Non-target lesions. All other lesions (or sites of disease) including any measurable lesions over and above the 5 target lesions should be identified as **non-target lesions** and should also be recorded at baseline. Measurements of these lesions are not required, but the presence, absence, or in rare cases unequivocal progression of each should be noted throughout follow-up.

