## 3. PATIENT SELECTION

### 3.1. Eligibility Criteria

- 3.1.1 Patients must have histologically or cytologically confirmed metastatic invasive breast cancer that is negative for the estrogen receptor (ER), progesterone receptor (PR) and HER2 by institutional guidelines.
- 3.1.2 Patients must have measurable disease (RECIST 1.1).
- 3.1.3 Patients must have had exposure to at least 1 and no more than 3 prior chemotherapy regimens for the treatment of metastatic breast cancer.
- 3.1.4 Patients must consent to both a pretreatment and a post-treatment mandatory research biopsy prior to enrolling on trial, and therefore, must have tissue (excluding bone or brain) that is amenable to biopsy.
- 3.1.5 Age  $\geq 18$  years. Because no dosing or adverse event data are currently available on the use of trametinib monotherapy or in combination with GSK2141795 in patients  $< 18$  years of age, children are excluded from this study, but will be eligible for future pediatric trials.
- 3.1.6 ECOG performance status 0-1 ([Appendix A](#)).

- 3.1.7 Life expectancy of greater than 3 months.
- 3.1.8 Able to swallow and retain orally-administered medication and does not have any clinically significant gastrointestinal abnormalities that may alter absorption such as malabsorption syndrome or major resection of the stomach or bowels.
- 3.1.9 All prior treatment-related toxicities must be CTCAE v5 grade  $\leq 1$  (except alopecia) at the time of enrollment.
- 3.1.10 Patients must have normal organ and marrow function as defined below:
- Absolute neutrophil count  $\geq 1,500/\text{mcL}$
  - Platelets  $\geq 75,000/\text{mcL}$
  - Total bilirubin  $\leq 1.5 \times$  institutional upper limit of normal
  - AST(SGOT)/ALT(SGPT)  $\leq 2.5 \times$  institutional upper limit of normal
  - LVEF  $\geq$  institutional lower limit of normal by ECHO or MUGA
  - Serum creatinine  $\leq 1.5 \text{ mg/dL}$  OR calculated creatinine clearance (Cockcroft-Gault formula)  $\geq 50 \text{ mL/min}$  OR 24-hour urine creatinine clearance  $\geq 50 \text{ mL/min}$
- 3.1.11 Patients must have controlled blood pressure with a systolic blood pressure  $< 140 \text{ mmHg}$  and diastolic  $< 90 \text{ mmHg}$ . Anti-hypertensive medications are permitted.

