- 3.1.12 Patients must be at least 4 weeks from last radiation dose. Patients must be at least 4 weeks from last chemotherapy, targeted therapy, or biologic therapy (exception allowed for a 2 week washout for patients who were on chemotherapy at less than a standard of care dose, as long as all other eligibility criteria are met). Patients must be at least 4 weeks from last surgical procedure and recovered from all post-operative complications.
- 3.1.13 The effects of trametinib monotherapy or trametinib in combination with GSK2141795 on the developing human fetus are unknown. For this reason, women of child-bearing potential and men must agree to use adequate contraception (hormonal or barrier method of birth control; abstinence) prior to study entry and for the duration of study participation. Should a woman become pregnant or suspect she is pregnant while she or her partner is participating in this study, she should inform her treating physician immediately. Men treated or enrolled on this protocol must also agree to use adequate contraception prior to the study, for the duration of study participation, and 4 months after completion of trametinib monotherapy or in combination with GSK2141795 administration.
- 3.1.14 Ability to understand and the willingness to sign a written informed consent document.

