## **4. REGISTRATION PROCEDURES**

### **4.1. General Guidelines**

OSU patients will be registered by the OSU research coordinator, as per their standard practice.

Subsite patients will have eligibility verified and will be entered on study centrally at the *The Ohio State University* by the Subsite Coordinator, [name]. All sites should call the Subsite Coordinator at [contact] to verify enrollment availability. The required forms,

Enrollment Form and Eligibility Screening Worksheet can be found in the Supplemental Forms Document.

Following registration, patients should begin protocol treatment within 5 days. Issues that would cause treatment delays should be discussed with the Principal Investigator. If a patient does not receive protocol therapy following registration, the patient's registration on the study may be canceled. The Subsite Coordinator should be notified of cancellations as soon as possible.

Except in very unusual circumstances, each participating institution will order DCTD-supplied agents directly from CTEP. Agents may be ordered by a participating site only after the initial IRB approval for the site has been forwarded by the Coordinating Center to the CTEP PIO ([contact]) except for Group studies.

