### 11.1.3 Methods for Evaluation of Measurable Disease

All measurements should be taken and recorded in metric notation using a ruler or calipers. All baseline evaluations should be performed as closely as possible to the beginning of treatment and never more than 4 weeks before the beginning of the treatment.

The same method of assessment and the same technique should be used to characterize each identified and reported lesion at baseline and during follow-up. Imaging-based evaluation is preferred to evaluation by clinical examination unless the lesion(s) being followed cannot be imaged but are assessable by clinical exam.

Clinical lesions Clinical lesions will only be considered measurable when they are superficial (*e.g.*, skin nodules and palpable lymph nodes) and  $\geq 10$  mm diameter as assessed using calipers (*e.g.*, skin nodules). In the case of skin lesions, documentation by color photography, including a ruler to estimate the size of the lesion, is recommended.

Chest x-ray Lesions on chest x-ray are acceptable as measurable lesions when they are clearly defined and surrounded by aerated lung. However, CT is preferable.

Conventional CT and MRI This guideline has defined measurability of lesions on CT scan based on the assumption that CT slice thickness is 5 mm or less. If CT scans have slice thickness greater than 5 mm, the minimum size for a measurable lesion should be twice the slice thickness. MRI is also acceptable in certain situations (*e.g.* for body scans).

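### An irradiated lesion can be a target lesion without documented progression since radiation and, under the 2-week chemotherapy washout only, the baseline scan can precede the last chemotherapy dose.

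*Combined protocol and SAP*

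**What the plan says.** Criterion 3.1.2 requires RECIST 1.1 measurable disease. Section 11.1.2 then says that "Tumor lesions that are situated in a previously irradiated area may be considered measurable". It does not ask for growth after radiation. Its target-lesion rules take measurable lesions, up to 2 per organ and 5 in total, by size, organ representation and reproducibility; prior irradiation plays no part.

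The washout rules are in criterion 3.1.12:
- Radiation: "Patients must be at least 4 weeks from last radiation dose".
- Systemic therapy, general rule: "Patients must be at least 4 weeks from last chemotherapy, targeted therapy, or biologic therapy".
- Systemic therapy, exception: "exception allowed for a 2 week washout for patients who were on chemotherapy at less than a standard of care dose".

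Section 11.1.3 asks for baseline evaluation close to treatment start and "never more than 4 weeks before the beginning of the treatment". Footnote 2 of the Study Calendar (Section 10) says "Tumor measurements within 4 weeks of first dose". Neither ties the scan to the end of prior therapy. Section 4.1 adds that "Following registration, patients should begin protocol treatment within 5 days".

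Section 11.1.4.1 scores a fall of 30% or more from the baseline sum of diameters as a partial response, whatever its cause. Section 13.3 tests a response rate of 5% against 20% in a single arm, continuing with at least 1 responder in 12 and declaring activity with at least 4 in 37.

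**The concern.** A single-arm response rate is credible only if shrinkage from baseline can be attributed to the study drug. Two rules, followed exactly, weaken that link.

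The first concerns radiation. A lesion treated 28 days before the first dose can be measured at baseline while still regressing. If it makes up all or most of the target sum, continued regression can reach 30% and be counted for trametinib. No other section closes this gap. The one rule about disease status after local therapy, criterion 3.2.6 on treated brain metastases, requires absence of progression and serves a different purpose.

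The second concerns scan timing in patients on the 2-week washout exception. Their baseline scan may precede their last chemotherapy dose, so change from baseline can include chemotherapy effect.

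There is no control arm to offset such responses. With thresholds of 1 in 12 and 4 in 37, a single misattributed response can change either decision.

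**Working it through.** **Timeline (day 0 = first dose of trametinib).**
- The baseline scan is no earlier than day -28 (Sections 10 and 11.1.3).
- Radiation: the last dose is no later than day -28, so the scan cannot precede it. The risk is delayed regression after baseline.
- Chemotherapy, 4-week rule: the last dose is no later than day -28, so the scan cannot precede it.
- Chemotherapy, 2-week exception: the last dose may be as late as day -14, so a day -28 scan precedes it by up to 28 - 14 = 14 days. Criterion 3.1.12 does not name the date to which washout is counted. If that date is registration and treatment starts 5 days later (Section 4.1), the gap is up to 28 - (14 + 5) = 9 days.

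**The plan's own design.** Stage 1 is read as monotherapy responses, although one sentence in Section 13.3 refers to combination therapy. With response probability p,

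P(declare active) = Σ over x ≥ 1 of P[Bin(12, p) = x] × P[Bin(25, p) ≥ 4 - x].

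At p = 0.05:

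| Stage 1 responders | Probability | P(enough in stage 2) | Product |
|---|---|---|---|
| 1 | 0.3413 | 0.1271 | 0.0434 |
| 2 | 0.0988 | 0.3576 | 0.0353 |
| 3 | 0.0173 | 0.7226 | 0.0125 |
| 4 or more | 0.0022 | 1 | 0.0022 |

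The sum is 0.0935 (0.09347 before rounding, so 9.3%). At p = 0.20 the same formula gives 0.902. Both agree with the stated 10% type I error and 90% power.

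**One spurious response among the 37, the other 36 patients at 5%.**
- It falls in the last 25 patients with probability 25/37. At least one genuine response in the first 12 and at least 3 in total are then needed: 0.2053.
- It falls in the first 12 with probability 12/37. Stage 1 is then passed automatically and at least 3 genuine responses in 36 are needed: 0.2679.
- Total: (25/37)(0.2053) + (12/37)(0.2679) = 0.1387 + 0.0869 = 0.226.

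The same calculation with two spurious responses gives 0.450.

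**If the 5% null already contains non-drug responses.** Suppose trametinib is inactive and carry-over, at rate s per patient, is the only source of responses. Putting p = s into the first formula gives:

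| Assumed s | P(declare active) |
|---|---|
| 0.5% | about 0% |
| 2% | 0.5% |
| 4% | 4.9% |
| 5% | 9.3% |
| 6% | 15.1% |

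The documents give no value for s; the range is an assumption. On this reading the planned 10% is exceeded only near the top of it.

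**Dilution.** If the irradiated lesion is a fraction w of the baseline sum and the other target lesions do not change, it must shrink by 30%/w to give a partial response. That is 30% when it is the only target lesion and 60% when it is half the sum. It is impossible when w is below 0.3.

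**The case against.** The strongest reply is that the effect may be small.
- A partial response is judged on the whole target sum, needs the absence of new lesions and of non-target progression, and is subject to confirmation (Section 11.1.4.3). An irradiated lesion must therefore dominate the sum.
- Section 13.3 describes responses under the 5% null as due to chance, which can be read as already covering non-drug responses.
- Section 11.1.3 asks for imaging close to treatment start, the irradiated-lesion note is permissive and not automatic, and responses are reviewed independently (Section 11.1.7).

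The dilution and null-rate arguments stand, and they limit how far the size can be pressed. The safeguards do not remove the problem: confirmation shows that shrinkage lasted and not what caused it, a day -28 scan remains allowed, and the review carries no rule on irradiated lesions. RECIST 1.1 is cited generally, but the protocol's own note is explicit and unconditional.

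Three stronger readings are tempting and not supported:
- A reader might infer that any patient's baseline scan can precede the last chemotherapy. Under the 4-week rule it cannot.
- A reader might infer that the scan-timing error always favors trametinib. Growth between an early scan and day 0 would make a 30% fall harder to reach.
- A reader might assume that 5-20% of patients have irradiated target lesions and 10-30% of those show carry-over, and so quote a false-positive rate of 12% to 50%. The documents give neither input, and that calculation ignores dilution and confirmation and adds carry-over to a full 5% rate.

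**Conclusion.** The point holds as a gap in the measurement rules. Delayed radiation shrinkage can be scored as a trametinib response, and for 2-week-washout patients alone the change from baseline may include chemotherapy effect. How often either occurs cannot be learned from the documents. The rise from 9.3% to about 23% illustrates sensitivity to one spurious response; it assumes a 5% response rate in the other 36 patients and is lower if the null already includes non-drug responses. It is not an estimate of the trial's error rate. The correction is still worth making, because the final threshold is 4 responders and the change is small.

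A reader might also infer that the primary endpoint should be re-scored. Section 13.2 reports in the past tense that 50 patients were consented in order to enroll 37 evaluable ones. Reclassifying their responses now would change the primary endpoint after the fact in an open-label trial, and no section requires sites to collect the scans needed to show post-radiation growth. A sensitivity analysis is the supportable step for them.

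**What to change.** - **Section 11.1.2:** amend the note so that a lesion in a previously irradiated area is measurable, and can be a target lesion, only if progression of that lesion was documented after the radiation. Criterion 3.1.2 then inherits the condition.
- **Sections 10 and 11.1.3:** keep the 4-week window and add that the baseline tumor scan must follow the last dose of prior anticancer therapy.
- **Patients already enrolled:** have the independent review under Section 11.1.7 flag each responder with an irradiated target lesion that lacks documented later progression, or with a baseline scan dated before the last prior therapy. Report the response rate, its exact 95% interval and the 4-of-37 decision with and without these responders, as a sensitivity analysis specified before the review begins.

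Sample size and decision thresholds do not change. The cost is a few sentences of protocol text, the occasional exclusion of a patient whose only measurable lesion was recently irradiated, later scan timing for a few 2-week-washout patients, and retrieval of radiation dates, chemotherapy dates and any available pre-baseline imaging for the responders. Where that imaging is missing, the responder should be listed as unverified.
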